Fax: PPD

COORDINATING INVESTIGATOR'S AGREEMENT

Coordinating Investigator Agreement and Signature:

I have read and agree to Protocol F-FR-00250-105 entitled Efficacy of the diosmectite (Smecta®) in the symptomatic treatment of acute diarrhoea in adults. A multicentre, randomised, double blind, placebo-controlled, parallel groups study. I am aware of my responsibilities as a coordinating investigator under the guidelines of Good Clinical Practice (GCP), local regulations (as applicable) and the study protocol. I agree to conduct the study according to these guidelines and to appropriately direct and assist the staff under my control, who will be involved in the study.

NAME: PPD

TITLE: COORDINATING
INVESTIGATOR

SIGNATURE:

DATE:

OFFICE: Délégation à la Recherche
Centre Hospitalier Régional Universitaire de Lille
[name]
[name]
France Cedex

SUMMARY OF CHANGES

The current version of the protocol was released on 07 January 2019 and includes Amendment 4. The corresponding amendment form was prepared and is provided in [Appendix 6 \(Table 1\)](#).

Table 1 List of Protocol Amendments

| Amendment | Release date | Amendment form |
|------------------|---------------------|----------------------------|
| 1 | 25 January 2016 | Appendix 4 |
| 2 | 10 March 2016 | Appendix 5 |
| 3 | 08 August 2017 | Appendix 6 |
| 4 | 07 January 2019 | Appendix 7 |

SYNOPSIS

| | |
|---|--|
| NAME OF SPONSOR/COMPANY: IPSEN PHARMA SAS | |
| Name of finished product: SMECTA® | |
| Name of active ingredient(s): Diosmectite- BN 00250 | |
| Title of study: EFFICACY OF DIOSMECTITE (SMECTA®) IN THE SYMPTOMATIC TREATMENT OF ACUTE DIARRHOEA IN ADULTS. A MULTICENTRE, RANDOMISED, DOUBLE BLIND, PLACEBO-CONTROLLED, PARALLEL GROUPS STUDY. Study number: F-FR-00250-105 | |
| Number of planned centres: 90 centres in 6 countries, including Algeria, Czech Republic, Poland, Tunisia, Lebanon and Egypt. | |
| Planned study period: December 2015 to September 2019 | Phase of development: Phase IV |
| Objectives: | |
| Primary: | |
| 
 • To demonstrate that diosmectite efficacy is superior to placebo regarding time to recovery of an acute diarrhoea episode presumed of infectious origin in adult subjects. | |
| Secondary: | |
| 
 • To demonstrate that diosmectite efficacy is superior to placebo regarding other efficacy criteria. • To assess the clinical tolerance of diosmectite versus placebo. | |
| Methodology: | |
| 
The study is a multicentre, prospective, double blind, placebo-controlled randomised comparative study. Efficacy and safety of diosmectite (administered at a dose and treatment regimen in line with the Diosmectite Beaufour Summary of Product Characteristics (SmPC) approved in France (the daily dosage can be doubled at the beginning of treatment for acute episode), i.e. 2 sachets containing 3 g of diosmectite each, three times a day (TID), a minimum of 24 sachets to be taken in 4 or 5 days and with a maximum of 48 sachets to be taken in 8 or 9 days) will be evaluated in adult subjects with a recent episode of acute diarrhoea presumed of infectious origin.
 | |
| Therapeutic schema: | |
| Two sachets (TID): 6 sachets per day (active or placebo): | |
| 
 • From Day 1 to Day 4 or Day 5: 
 - Mandatory treatment period = 24 sachets. • From Day 5 to Day 8 or Day 9: 
 - If one formed stool is followed by a nonwatery stool, i.e. recovery, the treatment is stopped. - In any case, treatment stops after a maximum of 48 sachets have been taken | |

At Visit 1, subjects will be blindly randomised to one of the two treatment groups (either active or placebo according to the randomisation list). Each randomised subject will receive a treatment box containing 48 sachets.

The treatment can be stopped after 4 days in case of 1 formed stool followed by a nonwatery stool. At Visit 2 (Day 5 or Day 6), a physical examination will be performed and safety will be assessed.

In case the subject has not recovered from diarrhoea at Visit 2, he/she will prolong the treatment with a maximum of 48 sachets up to Day 8 or Day 9 at the latest. For these subjects only, a third visit (Visit 3; Day 9 or Day 10) is planned.

Number of subjects planned:

A total of 726 assessable subjects are planned to be included in the study.

As it is assumed 5% subjects withdrawn without recovery and a maximum of 10% nonevaluable subjects, 854 subjects (427 per treatment group) will have to be randomised in order to achieve an 80% power.

Diagnosis and criteria for inclusion:**Inclusion criteria:**

- (1) Provision of written informed consent prior to any study related procedures,
- (2) male or female subject (outpatient) legally considered as an adult (age of majority). In Czech Republic the upper limit of age will be 70 years inclusive.
- (3) subject has a diagnosis of acute diarrhoea presumed of infectious origin, defined as:
 - the passage of 3 or more unformed loose or watery stools (rated according to the Bristol scale) per day without associated alarm symptoms*
 - having started within 48 hours before Visit 1 (first study drug intake time).
- (4) subject has, usually, normal bowel habits (Rome III criteria)** , i.e. at least 3 stools per week and no more than 3 stools per day,
- (5) subject must be willing and able to comply with study restrictions and willing to return to the clinic for the follow up evaluation(s) as specified in the protocol.

*Symptoms considered as alarm symptoms are identified in the exclusion criteria (1)

Exclusion criteria:**Exclusion criteria related to acute diarrhoea episode:**

- (1) At least one of the following alarm symptoms*
 - Bloody diarrhoea*,
 - pus in the stools*,
 - fever $\geq 38.0^{\circ}\text{C}$ *

- moderate or severe dehydration according to World Health Organisation (WHO) definition, requiring intravenous (IV) rehydration*,
- repeated vomiting*,
- persistent abdominal pain*

*These symptoms are considered as alarm symptoms

- (2) other episode of acute watery diarrhoea within the previous 30 days,
- (3) persistent diarrhoea, defined as acutely starting episode of diarrhoea lasting more than 14 days,
- (4) history of chronic diarrhoea (Rome III criteria); i.e. 3 or more loose or watery stools per day for at least 12 weeks, consecutive or not, in the preceding 12 months,
- (5) traveller's diarrhoea defined as a diarrhoeal episode due to contamination experienced by subjects having travelled in at risk countries, or coming from abroad and experiencing locally an acute diarrhoea episode, occurring usually within the first 2 weeks of the stay in a foreign environment.

Exclusion criteria related to drugs:

- (6) Diarrhoea suspected to be induced by drug, for example:
 - antibiotic therapy, including Clostridium difficile-induced diarrhoea, within 1 week before entry in the study,
 - laxative agent,
 - thyroid hormone (at a nonstabilised dosing),
 - colchicine intake, etc...
- (7) anti-diarrhoeal agent intake during the last month,
- (8) any subject requiring repeated intake of a drug with a narrow therapeutic margin (for example, digoxin, theophylline, etc...),
- (9) history of hypersensitivity to diosmectite or its excipients or placebo components,
- (10) subject likely to require treatment during the study with drugs that are not permitted by the study protocol (for example, antibiotic agent, anti-diarrhoeal agent, antiemetic drug, antispasmodic drug),
- (11) use of any investigational medication within the last 30 days before entering this study,
- (12) subject who previously entered in a clinical study within the past 30 days.

Other Digestive Exclusion criteria:

- (13) History of gastric or intestinal resection, vagotomy,
- (14) known digestive malabsorption disease, including coeliac disease
- (15) known lactose intolerance,
- (16) any suspicion of abdominal surgery need,
- (17) known inflammatory bowel disease.

Other Exclusion criteria:

- (18) Known Human immunodeficiency virus (HIV) positive status,

- (19) known or suspected immunosuppression,
- (20) known severe renal or hepatic insufficiency,
- (21) Uncontrolled diabetes of all types and non insulin dependant diabetes during first 6 months of medical treatment and other known endocrine disease,
- (22) history of, or known current, problems with alcohol abuse and/or known drug addiction (cocaine, heroin, hashish...),
- (23) previous enrolment in this study,
- (24) any mental condition rendering the subject unable to understand the nature, scope and possible consequences of the study, and/or evidence of an uncooperative attitude.
- (25) Pregnant or lactating women

Test product, dose, mode of administration:

The test product consists of sachet of powder for suspension for oral use containing 3 g of diosmectite.

Diosmectite will be presented in sachets according to the following composition:

- active substance:
 - diosmectite: 3 g
- other components:
 - vanillin, saccharin sodium and glucose monohydrate.

Each sachet will be mixed with water prior to administration

The regimen below will be 2 sachets TID:

- 2 sachets in the morning,
- 2 sachets at mid-day,
- 2 sachets in the evening.

Duration of treatment:

This study will consist of an inclusion visit, i.e. Visit 1 (the subject will be randomised and start treatment that day) and a 4- to 9-day dosing period. Subjects are expected to take the study treatment in this study with a minimum of 24 sachets to be taken in 4 days or 5 days and with a maximum of 48 sachets to be taken in 8 or 9 days. Visit 2 will be on Day 5 or Day 6 and Visit 3 will be on Day 9 or Day 10.

The subject's participation in the study will be considered to have ended when the subject will have recovered from diarrhoea, defined as one formed stool followed by a nonwatery stool and when the last follow-up visit is performed.

The overall duration of the study for each subject will be 5 to 6 days (if subject has recovered by Visit 2) or 9 to 10 days (duration of study treatment can be from 4 to 9 days).

Reference therapy, dose and mode of administration:

Placebo:

Placebo will be presented in sachets according to the following composition:

- titan dioxide, Spray dried liquid glucose, vanillin, saccharin sodium, glucose monohydrate,

- caramel colouring E 150 B.

The regimen will be the same as for the active treatment.

Criteria for evaluation:**Efficacy:**

Primary endpoint and evaluation: time to recovery, defined as the time (hours, minutes) from the 1st study treatment intake to the first formed stool (this formed stool must have been followed by a nonwatery stool). Consistency will be rated according to the Bristol scale.

Secondary endpoints and evaluations:

- abdominal pain intensity (rated with a 5-point ordinal scale: 0 = absent, 1 = mild, 2 = moderate, 3 = severe, 4 = very severe) per 12-hour period,
- time (hours, minutes) from diarrhoea onset to recovery defined as first formed stool followed by a nonwatery stool
- time (hours, minutes) from first watery stool to the first formed stool
- time (hours, minutes) from the 1st study treatment intake to the last watery stool,
- number of stools, per 12-hour period,
- number of watery stools, per 12-hour period,
- Percentage of subjects with associated symptoms such as nausea, vomiting, abdominal pain and anal irritation, per 12-hour period.

Safety:

Occurrence of adverse events (AEs) reported by the subject from the time that the subject gives informed consent until 7 days after the end of the study treatment. Vital signs (blood pressure, heart rate in sitting position, respiratory rate, body temperature and body weight) measurement at each visit, physical examination findings and measurements, at each visit, body height (at Visit 1 only), concomitant medication usage throughout the study.

Microbiological Tests:

A fresh stool will be collected as soon as possible after inclusion for microbiological laboratory testing (for virology, bacteriology and parasitology testing) in order to determine the microbiological status of this acute diarrhoea episode, i.e. the absence/presence of the following faecal pathogens:

Virology testing

- rotavirus,
- adenovirus,
- norovirus,

Bacteriology and parasitology testing

- enteropathogenic and enterotoxigenic Escherichia coli (E. coli),
- staphylococcus aureus,

- shigella,
- salmonella,
- campylobacter,
- yersinia enterocolitica,
- amoebiasis (entamoeba histolytica),
- giardia/lamblia.

Statistical Methods:**Sample size rationale:**

Assuming a median time to recovery of 55 hours in the active group and 70 hours in the placebo group (corresponding to a difference of 15 hours as evidenced in the Khediri et al study [Gastroenterology Research and Practice, Volume 2011, Article ID 783196, <http://dx.doi.org/10.1155/2011/783196>]), 363 subjects per treatment group (726 in total) will be required in order to detect such a difference using a two-sided Gehan-Wilcoxon test at a significance level of 5% and a power of 80%.

It is assumed a maximum of 5% of subjects prematurely withdrawn without recovery and a maximum of 10% of nonevaluable subjects (because of poor/incomplete diary completion). Accordingly, 854 subjects (427 per treatment group) will be required in order to achieve an 80% power.

Planned Statistical analyses:**Populations:**

Following study populations will be defined:

- Intent to treat (ITT) population: all randomised subjects analysed according to the arm to which they were randomised.
- Safety population: all randomised subjects with at least one dose of study medication analysed according to the actual treatment received.
- Modified Intent to treat (mITT) population: all randomised subjects who received at least one dose of study medication and have at least one efficacy assessment for the primary endpoint***. Subjects will be analysed according to the arm to which they were randomised.
- Per protocol (PP) population: all subjects in the mITT population for whom no major protocol violations/deviations occurred.

***The efficacy assessment will be based on the Diary evaluation booklet (DEB), therefore subjects who have not filled in the DEB will be excluded from the efficacy analysis.

All efficacy endpoints and subject demographics will be evaluated in the ITT population. Treatment administration/compliance and safety will be analysed in the Safety population. Supportive analysis using mITT and PP population will be carried out.

Primary endpoint:

The primary endpoint (time from the 1st treatment dose intake (T_0) to recovery defined as first formed stool followed by a nonwatery stool, in hours) will be analysed using a time to event analysis (Kaplan-Meyer method) and the comparison between the two treatment groups will be done using Gehan-Wilcoxon test, as the efficacy of the active product is

expected quickly after study intake. In this analysis, subjects prematurely withdrawn or ending the study without recovery will be censored.

Estimated medians and quartiles will be provided with their 95% confidence intervals (CIs), leading to a comparison of the time between groups where 25, 50 and 75% of the subjects have recovered.

Descriptive statistics for efficacy evaluation may be provided by country, season, absence/presence of faecal pathogens.

Secondary endpoints:

The secondary endpoints related to time to event (efficacy variables b, c and d) will be analysed using the same methodology as for the primary efficacy endpoint.

Regarding the secondary endpoints based on number of stools per 12-hour period, a repeated measurement model of number of stools during the post baseline period will be fitted using the analysis of covariance (ANCOVA) method if data warrant. The model will include as fixed effects number of stools 24 hours before randomisation (baseline), treatment, time point (12-hour period) and the treatment by time point interaction effect. The same analysis will be performed for number of watery stools.

Regarding the efficacy endpoints related to binary data, a general linear mixed model will be fitted if data warrant in order to evaluate the treatment effect at each 12-hour period, according to the same methodology as described above.

Safety endpoints:

AEs per treatment group will be described for the Safety population.

AEs will be coded according to Medical Dictionary for Regulatory Activities (MedDRA) and AE listings will be presented by subject, system organ class and preferred term.

Incidence of all reported AEs/treatment emergent AEs (TEAEs) and SAEs will be tabulated by treatment group and overall. In addition, summary tables will be presented by maximum intensity, drug relationship and AEs/TEAEs associated with premature withdrawal of study medication.

Concomitant medication will be coded by using WHO Drug Dictionary and will be summarised by treatment group and overall with the number and percentage of subjects receiving concomitant medication by drug class and preferred drug name.

Summary statistics (mean, median, SD and range as appropriate) by treatment group and overall will be presented for vital signs (blood pressure, heart rate in sitting position, respiratory rate, body temperature, body weight), at each assessment with change from baseline.

TABLE OF CONTENTS

| | |
|--|-----------|
| LIST OF ABBREVIATIONS..... | 16 |
| 1 BACKGROUND INFORMATION | 18 |
| 1.1 Introduction..... | 18 |
| 1.2 Name and Description of Investigational Medicinal Product..... | 19 |
| 1.3 Findings from Nonclinical and Clinical Studies..... | 19 |
| 1.4 Known and Potential Risks and Benefits to Human Subjects | 20 |
| 1.5 Selection of Investigational Medicinal Products and Dosages..... | 21 |
| 1.6 Compliance Statement..... | 21 |
| 1.7 Population to Be Studied | 21 |
| 2 PURPOSE OF THE STUDY AND STUDY OBJECTIVES..... | 22 |
| 2.1 Purpose of the Study | 22 |
| 2.2 Study Objectives | 22 |
| 3 STUDY DESIGN..... | 23 |
| 3.1 General Design and Study Schema | 23 |
| 3.2 Primary and Secondary Endpoints and Evaluations | 23 |
| 3.2.1 Primary Efficacy Endpoint and Evaluation | 23 |
| 3.2.2 Secondary Efficacy Endpoints and Evaluations | 24 |
| 3.2.3 Safety Endpoints and Evaluations | 24 |
| 3.3 Randomisation and Blinding | 24 |
| 3.4 Study Treatments and Dosage | 25 |
| 3.5 Study Duration | 26 |
| 3.6 Stopping Rules and Discontinuation Criteria | 26 |
| 3.7 Investigational Medicinal Product Preparation Storage and Accountability | 26 |
| 3.7.1 Investigational Medicinal Product Storage and Security | 26 |
| 3.7.2 Investigational Medicinal Product Preparation | 26 |
| 3.7.3 Investigational Medicinal Product Accountability | 26 |
| 3.8 Maintenance of Randomisation and Blinding..... | 27 |
| 3.9 Source Data Recorded on the Case Report Form..... | 27 |
| 4 SELECTION AND WITHDRAWAL OF SUBJECTS | 29 |
| 4.1 Inclusion Criteria..... | 29 |
| 4.2 Exclusion Criteria | 29 |

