3.2 Primary and Secondary Endpoints and Evaluations

3.2.1 *Primary Efficacy Endpoint and Evaluation*

The primary efficacy endpoint is the time to recovery, defined as time from the 1st study treatment intake recorded in the electronic case report form (eCRF) to the first formed stool followed by a nonwatery stool, recorded in the DEB.

Consistency will be rated according to the Bristol scale [13].

3.2.2 *Secondary Efficacy Endpoints and Evaluations*

The secondary endpoints are the following:

- (a) abdominal pain intensity (rated with a 5-point ordinal scale: 0 = absent, 1= mild, 2 =moderate, 3 = severe, 4= very severe) per 12-hour period, recorded in the DEB
- (b) time (hours, minutes) from diarrhoea onset to recovery defined as first formed stool followed by a nonwatery stool, recorded in the DEB
- (c) time (hours, minutes) from first watery stool to the first formed stool, recorded in the DEB
- (d) time (hours, minutes) from the 1st study treatment intake recorded in the eCRF to the last watery stool recorded in the DEB,
- (e) number of stools, per 12-hour period, recorded in the DEB
- (f) number of watery stools, per 12-hour period, recorded in the DEB
- (g) percentage of subjects with associated symptoms such as nausea, vomiting, abdominal pain and anal irritation, per 12-hour period, recorded in the DEB*.

*Nausea, vomiting, abdominal pain and anal irritation, per 12-hour period will be recorded in the DEB. The percentage of subjects will not be recorded in the DEB.

3.2.3 *Safety Endpoints and Evaluations*

The safety and tolerability of diosmectite will be assessed throughout the study by evaluating adverse events (AEs) recorded from subject from the time that the subject gives informed consent until 7 days after the end of the study treatment, vital signs measurements, and physical examination results, and concomitant medication usage.

3.3 **Randomisation and Blinding**

The secondary packaging is similar allowing the blinded conditions of the study to be maintained. Subjects and investigators will remain blinded to treatment assignment during the study.

The sponsor's randomisation manager who is a statistician independent from the study will prepare the master list of randomisation numbers for this study. It will be produced in blocks, in a balanced 1:1 ratio. After eligibility is confirmed, at Visit 1 (Day 1), subjects will be assigned a randomisation number and to the associated treatment arm, in sequential order within each centre.

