10.2 Sample Size Determination

Assuming a median time to recovery of 55 hours in the active group and 70 hours in the placebo group (corresponding to a difference of 15 hours as evidenced in the Khediri et al study [7], 363 evaluable subjects per treatment group (726 in total) will be required in order to detect such a difference using a two-sided Gehan- Wilcoxon test at a significance level of 5% and a power of 80%.

It is assumed a maximum of 5% subjects prematurely withdrawn without recovery and a maximum of 10% nonevaluable subjects (because of poor/incomplete diary (DEB) completion).

Accordingly, 854 subjects (427 per treatment group) have to be randomized in order to achieve an 80% power

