Regarding the secondary endpoints based on number of stools per 12-hour period, a repeated measurement model of number of stools during the post baseline period will be fitted using the analysis of covariance (ANCOVA) method if data warrant. The model will include as fixed effects number of stools 24 hours before randomisation (baseline), treatment, time point (12-hour period) and the treatment by time point interaction effect. The residual variance-covariance pattern will be fitted using an unstructured matrix. In addition a cumulative number of stools per 12-hour period will be presented graphically.

The same analysis will be performed for number of watery stools. The model will include, as fixed effects, number of watery stools 24 hours before randomisation, treatment, time point (12-hour interval) and the treatment by time point interaction effect.

Regarding the efficacy endpoints related to binary data, a general linear mixed model will be fitted if data warrant in order to evaluate the treatment effect at each 12-hour period, according to the same methodology as described above.

In addition point estimate will be tabulated by treatment group and overall with their corresponding two-sided 95% CIs and when appropriate in terms of mean, SD, median and interquartile as well as the range.

More details will be given in the SAP.

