1.3.4 Planned sample size

Assuming a median time to recovery of 55 hours in the active group and 70 hours in the placebo group (corresponding to a difference of 15 hours as evidenced in the Khediri et al study [1]), 363 evaluable subjects per treatment group (726 in total) will be required in order to detect such a difference using a two-sided Gehan-Wilcoxon test at a significance level of 5% and a power of 80%.

It is assumed a maximum of 5% of subjects prematurely withdrawn without recovery and a maximum of 10% of non-evaluable subjects (because of poor/incomplete diary completion). Accordingly, 854 subjects (427 per treatment group) will be required in order to achieve an 80% power.

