Any stool with a missing evaluation consistency should be counted in the total number of stools per 12-hour period (if time of stool is not missing).

Any stool with a missing time, with a consistency evaluation and which is embedded within the same time interval will be counted in the number of stools for the considered time interval. The number of stools per 12-hour period during the post baseline period will be analysed with an analysis of covariance (ANCOVA) method with repeated measurements. The model will include number of stools 24 hours before randomisation (baseline) as covariate, treatment, time point (12-hour period until visit 3), the treatment by time point interaction as fixed effects and subject as random effect. The residual variance-covariance pattern will be fitted using an unstructured matrix (see SAS Syntax below). Adjusted means, 95% CIs and corresponding p-values of differences between diosmectite and placebo, derived from the model, will be displayed globally and for each time point.

CCI

[REDACTED]

If the model fails to converge, only time intervals with a sufficient number of patients could be included in the model.

In the event of gross violations from the normality assumptions (identified using the shape of the distribution and QQ plots of change from baseline overall and by visit) or from the covariance model assumptions or in case of convergence criterion fails to be reached, a non-parametric analysis will be used instead (Mann-Wilcoxon-Mann-Whitney test (see SAS syntax below)) at each time point separately.

CCI
[REDACTED]
[REDACTED]
[REDACTED]
[REDACTED]
[REDACTED]
[REDACTED]

In addition the cumulative number of stools per 12-hour period will be presented graphically using barcharts of means (\pm SEM) on observed values at each time point by treatment group.

(f) Number of watery stools, per 12-hour period.

The same analysis as described above will be performed for number of watery stools (corresponding to type 6 or 7). The model will include, as fixed effects, number of watery stools 24 hours before randomisation, treatment, time point (12-hour interval) and the treatment by time point interaction effect.

(g) Percentage of subjects with associated symptoms such as nausea, vomiting, abdominal pain and anal irritation, per 12-hour period.

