The proportion of subjects with at least one associated symptom will be displayed per treatment group and per 12-hour period, using data retrieved from the DEB for post baseline values and using data retrieved from the eCRF for baseline value (Presence of associated symptoms during the last 24 hours from the “History of current acute diarrhoea episode” page). Same results will be displayed for each symptom separately: nausea, vomiting, abdominal pain and anal irritation. To assess the treatment effect at each 12-hour period on associated symptoms overall and on each symptom separately, a non-linear mixed model will be used including treatment and status of subjects at baseline (With or without associated symptoms), time-point and treatment by time-point interaction as fixed effects and number of watery stools during 24h prior inclusion as covariate (see SAS Syntax below).

CCI
[REDACTED]
[REDACTED]
[REDACTED]
[REDACTED]
[REDACTED]
[REDACTED]
[REDACTED]
[REDACTED]
[REDACTED]

In addition the percentage of subjects (with at least associated symptom and for each symptom separately) per 12-hour period will be presented graphically using barcharts at each time point by treatment group.

3.2.2 *Safety*

All safety data will be included in the data listings and summary tables will be based on the safety population.

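### The stool-count models hold the baseline slope constant over all 12-hour periods, which costs some precision in the early per-period contrasts; a baseline-by-time-point term is a cheap improvement

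*Protocol*

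**What the plan says.** The term lists agree across the two documents.

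- **Stools, endpoint (e).** The Protocol (Synopsis and 10.4.5) lists "number of stools 24 hours before randomisation (baseline), treatment, time point (12-hour period) and the treatment by time point interaction effect" as fixed effects, with an unstructured residual covariance in 10.4.5. SAP 3.2.1.2 (e) keeps this: "The model will include number of stools 24 hours before randomisation (baseline) as covariate, treatment, time point (12-hour period until visit 3"), plus treatment by time point, a subject random effect and the unstructured matrix.
- **Watery stools, endpoint (f).** Protocol 10.4.5 and SAP 3.2.1.2 (f) list "number of watery stools 24 hours before randomisation, treatment, time point (12-hour interval) and the treatment by time point interaction effect".
- **Associated symptoms, endpoint (g).** SAP 3.2.1.2 (g) describes a non-linear mixed model "including treatment and status of subjects at baseline (With or without associated symptoms), time-point and treatment by time-point interaction as fixed effects", with the baseline watery-stool count as a further covariate.

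The only interaction with time in any list is that of treatment. The SAS code is redacted, so this rests on the written lists. SAP 3.2.1.2 (e) reports adjusted means, confidence intervals and p-values both overall and for each 12-hour period. SAP 3.1.4 makes only the primary analysis of the primary endpoint confirmatory.

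**The concern.** The covariate is a count over the 24 hours before randomisation. It should predict the first day of diary data fairly well. It should predict Day 5 to Day 9 poorly, because by then most subjects are expected to have recovered. The true slope of outcome on baseline should therefore fall from period to period.

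A model with one slope estimates a weighted average of the period slopes. With an unstructured covariance, the weights come from generalised least squares and favour periods with small residual variance, which tend to be the late ones. Early periods are then under-adjusted and, in some settings, the latest periods are over-adjusted. What is at stake is the width of the per-period intervals and the correction of chance baseline imbalance in the early periods.

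**Working it through.** **The plan's own figure.** Neither document gives a power or sample size for these models. The only calculation is for time to recovery ("Assuming a median time to recovery of 55 hours in the active group and 70 hours in the placebo group", two-sided 5%, 80% power). It reproduces:

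- Schoenfeld events: 4(1.96 + 0.8416)² / [ln(55/70)]² = 540.
- Divided by 0.75, the efficiency of Gehan-Wilcoxon relative to log-rank under exponential times: 720, against 726 stated.
- 726 / 0.85 = 854.

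It says nothing about the baseline term.

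**Formula.** Let b_k be the true baseline slope in period k, S the residual covariance matrix given treatment and baseline, and V the variance of the baseline count. With complete data:

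- common slope: b_c = (1'S⁻¹b) / (1'S⁻¹1)
- variance inflation of the period-k treatment contrast, against period-specific slopes: 1 + (b_k − b_c)² V / S_kk
- inflation with no baseline adjustment at all: 1 + b_k² V / S_kk

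**Inputs from the documents.** Medians of 55 and 70 h, 12-hour periods, 1:1 allocation.

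**Inputs assumed, because the documents give none.**

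- Exponential recovery.
- Subject severity u, gamma with mean 1 and variance 0.25, 0.5 or 1.0.
- Baseline count 3 + Poisson(3u).
- 12-hour counts Poisson(2u) before recovery, either constant or falling 10% per period, and Poisson(0.6) after recovery.

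**Results, nine complete periods (0-108 h).** Variance inflation in percent:

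| Stool rate | Severity variance | b at 0-12 h | Common b | 0-12 h | 12-24 h | 24-36 h | 36-48 h | 48-72 h | 96-108 h | All-period |
|---|---|---|---|---|---|---|---|---|---|---|
| Constant | 0.25 | 0.27 | 0.16 | 2 | 1 | 0 | 0 | 0 | 2 | 0 |
| Constant | 0.5 | 0.38 | 0.23 | 6 | 3 | 1 | 0 | 0-1 | 4 | 0 |
| Constant | 1.0 | 0.47 | 0.30 | 11 | 5 | 1 | 0 | 0-2 | 9 | 0 |
| Falling | 0.25 | 0.27 | 0.08 | 7 | 4 | 2 | 1 | 0 | 1 | 3 |
| Falling | 0.5 | 0.37 | 0.10 | 20 | 11 | 6 | 3 | 0-1 | 2 | 8 |
| Falling | 1.0 | 0.47 | 0.13 | 45 | 25 | 13 | 6 | 0-2 | 5 | 15 |

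One cell in full (falling rate, variance 0.5): b₁ = 0.374, b_c = 0.104, V = 7.41, S₁₁ = 2.76. The inflation is 1 + (0.270)² × 7.41 / 2.76 = 1.196. With no adjustment it would be 1 + (0.374)² × 7.41 / 2.76 = 1.376. The common slope therefore forfeits about half (0.196 / 0.376) of what adjustment could gain in that period.

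**Longer follow-up.** Extend to 216 h, with the diary ending at 108 h for subjects recovered by then. The added late periods pull the common slope down further. The 0-12 h inflation becomes 3 / 7 / 17% (constant rate) and 10 / 23 / 58% (falling rate). The upper figure is like discarding 1 − 1/1.58 = 37% of the sample for that one contrast.

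**Cross-check with a different model.** Assume correlations of 0.3 / 0.5 / 0.7 between baseline and the first period, halving every 24 h, AR(1) 0.6 within subject, and 10 to 18 periods. The first-period inflation is 4-6 / 11-18 / 23-42% with constant outcome SD and 7-9 / 24-29 / 63-79% with falling SD. In 1,500 simulated trials at correlation 0.5 (10 periods, falling SD), the mean treatment estimate was zero, its true value, under both models. The standard errors were 0.0709 (common slope) and 0.0638 (period-specific), a variance ratio of 1.24. The mechanism is confirmed; the size depends on the assumptions.

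**The case against.** **The early contrasts may matter least.** A reader might infer that adjustment is weakened just where the drug is expected to act. The documents do not support that. The Synopsis remark that efficacy is expected soon after intake is the reason for using the Gehan-Wilcoxon test on time to recovery; it makes no claim about stool counts in the first day. With exponential recovery at the planned medians, the gap between arms in the proportion unrecovered, 2^(−t/70) − 2^(−t/55), is 2.8 points at 12 h, 4.9 at 24 h, 7.6 at 48 h, and peaks at about 9 near 89 h. In the simulation above, the 0-12 h difference is about 0.01-0.03 stools, or 0.1-0.25 standard errors with 363 per arm. The standardised effect is largest around 36-72 h with a falling rate (inflation about 0-6%) and after 72 h with a constant rate (about 0.5-10%). This objection stands, and the point is confined to precision.

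**No bias in the counts.** A reader might also infer biased treatment effects. Randomisation protects the per-period count contrasts under either model. The planned model still adjusts for baseline, only less efficiently than it could.

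**Size is assumed.** This is also fair. With a constant rate and moderate heterogeneity the early loss is only a few percent.

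**The symptom model (g) is a different model.** The least-squares argument concerns linear models of counts. No calculation was made under the planned non-linear mixed model, so no loss is claimed for (g).

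**SAP contingencies.** On non-convergence the SAP may drop sparse intervals, which would reduce the inflation. It may also switch to per-period Wilcoxon tests, which list no baseline adjustment and would gain nothing from this change.

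**Conclusion.** The structural point holds for (e) and (f): each baseline count has one slope over all periods, while its predictive value should fade as subjects recover. The consequence is lost precision in per-period contrasts, mainly in the first 24-36 h. Under the stated assumptions the 0-12 h variance is about 2-17% larger with a constant stool rate and 7-58% larger with a rate falling 10% per period. The second model shows that stronger assumptions can exceed the upper figure. At 36-72 h the inflation is about 0-6%. The all-period contrast is unaffected with a constant rate and may lose up to about 15% with a falling one.

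The primary analysis is untouched, and the endpoints concerned are secondary and non-confirmatory. This is a low-cost improvement in efficiency, not an error in the plan.

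**What to change.** Before unblinding:

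- **(e) and (f):** in Protocol 10.4.5 (and the matching Synopsis text) and SAP 3.2.1.2, add the interaction of baseline count with time point, using the total count for (e) and the watery count for (f). Leave the other terms and the covariance as they are.
- **(g):** for consistency, add time-point interactions for both baseline symptom status and baseline watery-stool count, provided the model converges. The gain here has not been quantified.
- If only the SAP is changed, record it in SAP section 5, which at present declares no changes from the protocol.

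The cost is one extra degree of freedom per extra period for each covariate: 17 if the diary runs to 216 h (216 / 12 = 18 periods), with about 850 subjects. There is some added convergence burden in models that are already large. No new data are needed. The change does not help the per-period Wilcoxon fallback.
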